5 ENDPOINTS AND COVARIATES

Primary endpoint: Percent of patients with radiographic disease progression according to RECIST 1.1 at 6 months, defined as 180 days from initial treatment (C1/D1).

Secondary endpoints:

- (1) Incidence of toxicities
From initial treatment to end-of-treatment
- (2) Overall survival
Time from initial treatment to death

Exploratory endpoints:

- (1) Disease progression according to RECIST 1.1 versus iRECIST criteria
Percent of patients with radiographic disease progression at 6 months

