7 STATISTICAL METHODOLOGY

7.1 STATISTICAL PROCEDURES

Primary outcome: Progression-free survival

The proportion of patients in each arm who are progression-free at 6-months will be compared using a one-sided test of binomial proportions (equivalent to a Pearson's chi-squared test). If the assumptions of the Pearson's chi-squared test are not met, Barnard's exact unconditional test of equality will be used, as implemented in StatXact.

Patients unevaluable for progression at 6-months due to a non-progression related event will be excluded from analysis.

Statistical comparison of progression-free survival between the two treatment arms will be performed using a log-rank test, with estimation of the hazards ratio using a Cox proportional hazards model. A sensitivity analysis will include patients with an outcome of death due to another cause (other than progressive disease), which will be considered a competing event for progression. Analysis will be performed using the Fine and Gray (1999) approach.

Secondary outcome 1: Toxicity

All adverse events (AE) occurring on or after C1/D1 will be summarized by body systems and per grade according to NCI-CTCAE Version 4. Additionally, all serious adverse events (SAE) and events of clinical interest (ECI) will be listed separately and tabulated. ECIs for this trial include an overdose of pembrolizumab and an elevated AST or ALT lab value, as defined in section 6.2.3.2 of the protocol. All patients who receive any amount of trial treatment will be included in the analysis. The proportion of patients in each arm with toxicity will be compared using a chi-squared test or Barnard's exact unconditional test of equality as outlined above.

Secondary outcome 2: Overall survival

Overall survival will be calculated for each arm using a Kaplan-Meier estimate. Statistical comparison of overall survival between the two treatment arms will be performed using a log-rank test, with estimation of the hazards ratio using a Cox proportional hazards model. Patients with an outcome of death due to another cause (other than progressive disease) will be considered a competing event for death. Analysis will be performed using the Fine and Gray (1999) approach.

Exploratory outcome 1: RECIST 1.1 versus iRECIST

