Comparison of the proportion of patients who are progression-free at 6 months using iRECIST will be performed using the same method as for the primary endpoint of RECIST 1.1. McNemar's test will be used to estimate the concordance between RECIST 1.1 and iRECIST.

7.2 MEASURES TO ADJUST FOR MULTIPLICITY, CONFOUNDERS, HETEROGENEITY, ETC.

Since all primary and secondary endpoints are pre-specified, there will be no adjustment for multiple comparisons. In the context of a randomized clinical trial, the two treatment arms are expected to be balanced with regard to potential confounders, therefore, adjustment is generally not necessary.

References:

Fine, J. P., and R. J. Gray. 1999. A proportional hazards model for the subdistribution of a competing risk. *Journal of the American Statistical Association* 94: 496–509.

Proposed Tables

Table 1. Characteristics of patients at baseline

Characteristic	Pembrolizumab n = x	Pembrolizumab + Paricalcitol n = x	Total n = x
Age, y			
Median			
Range			
Sex, n (%)			
Female			
Male			
Race/ethnicity, n (%)			
Asian			
Black			
White			
Hispanic			
Other			
Study site, n (%)			
HonorHealth Research Institute			
City of Hope			
Atlantic Health System			
Baylor Scott and White Research Institute			
University of Kansas Medical Center			
Medical College of Wisconsin			
Pancreatic tumor location, n (%)			
Head			
Body			
Tail			
Unknown			
Site of metastatic disease, n (%)			
Liver			
Lung			
Peritoneum			
No. of metastatic sites, n (%)			
1			
2			
3			
>3			

Carbohydrate antigen (CA) 19-9			
Median, U/mL			
Range, U/mL			
Normal (0-35 U/mL), n (%)			
ULN to <59x ULN, n (%)			
≥59x ULN, n (%)			
Previous therapy, n (%)			
Radiation therapy			
Chemotherapy			
Whipple procedure			
Biliary stent			

Figure 1. (A) Progression-free survival by investigator-assessment, (B) Progression-free survival by independent assessment, (C) Overall survival

Table 2. Progression-free survival and overall survival in the intention-to-treat population

Efficacy variable	Pembrolizumab n = x	Pembrolizumab + Paricalcitol n = x	Hazard ratio or Response-rate ratio (95% CI)	P value
Progression-free survival by investigator-assessment				
RECIST 1.1				
Rate of progression-free survival, % (95% CI)				
6 mo				
12 mo				
Median progression-free survival, mo (95% CI)				
Progression-free survival by independent assessment				

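### SAP 7.1 states no analysis in which a death from a cause other than progressive disease counts as a progression-free survival event, so Figure 1 A/B and Table 2 would show time to progression with respect to those deaths

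*SAP*

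**What the plan says.** SAP 5 gives the primary endpoint as "Percent of patients with radiographic disease progression according to RECIST 1.1 at 6 months, defined as 180 days from initial treatment (C1/D1"). Death is not named. SAP 7.1 then heads the same outcome "Primary outcome: Progression-free survival" and, after the binomial test at 6 months, adds a time-to-event comparison: "Statistical comparison of progression-free survival between the two treatment arms will be performed using a log-rank test", with a Cox hazard ratio. It gives neither an event definition nor a censoring rule.

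The next sentence is the only one in that paragraph that deals with death: "A sensitivity analysis will include patients with an outcome of death due to another cause (other than progressive disease"). In that analysis, which uses the Fine and Gray method, the role given to such a death is not that of a failure: "which will be considered a competing event for progression".

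The output shells under Proposed Tables carry the progression-free survival label throughout. Figure 1 has panels ("A) Progression-free survival by investigator-assessment, (B) Progression-free survival by independent assessment, (C) Overall survival"). Table 2 is headed "Table 2. Progression-free survival and overall survival in the intention-to-treat population" and has rows for 6- and 12-month rates and medians, with a hazard-ratio column. SAP 7.1 names Kaplan-Meier only for overall survival; for progression-free survival it is implied by these shells.

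The protocol does not fill the gap. Protocol 8.3.4 plans only the binomial comparison at 180 days, and no part of Protocol 8.3 sets out a between-arm time-to-event analysis of progression-free survival.

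**The concern.** Progression-free survival is ordinarily read as time to progression or death from any cause. If other-cause deaths need a sensitivity analysis to bring them in, the main analysis presumably censors those patients or leaves them out. In the sensitivity analysis the death is a competing event, which is again not a failure. A patient who dies of another cause without progression would then be a failure in neither analysis.

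At stake is what the main efficacy table and figure mean. A reader would take the rates, medians and hazard ratios as progression-free survival and set them beside figures that include death. With 12 patients per arm, one or two such deaths are enough to move the curve visibly.

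**Working it through.** **The plan's own figure.** There is no planning figure for the time-to-event analysis. The only related one is Protocol 8.2: 12 per arm, 8% (1/12) v 58% (7/12) progression-free at 6 months, one-sided alpha 0.05, 90% power. Exact enumeration of the uncorrected Pearson test gives 90.1%, so it reproduces. It concerns the binary endpoint and neither supports nor weakens this point; it supplies the planning rates used below.

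**Direction.** Take one set of follow-up times and treat an other-cause death first as censored, then as an event. The risk sets are the same. Counting the death multiplies the Kaplan-Meier estimate by a further factor (1 − 1/n at risk), which is below 1. Censoring therefore never gives a lower curve than counting the death.

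**Illustrative arm of 12.** Two progressions at week 9, three at week 18, k other-cause deaths at week 12, the rest progression-free. Estimate at 6 months:

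| | Death censored | Death counted | Patient dropped |
|---|---|---|---|
| k = 1 | 10/12 × 6/9 = 55.6% | 10/12 × 9/10 × 6/9 = 50.0% | 9/11 × 6/9 = 54.5% |
| k = 2 | 10/12 × 5/8 = 52.1% | 10/12 × 8/10 × 5/8 = 41.7% | 8/10 × 5/8 = 50.0% |

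Dropping the patient is not uniformly upward: at week 10 with k = 1 it gives 9/11 = 81.8% against 10/12 = 83.3%.

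**Size under stated assumptions.** The documents give no rate of death without progression. Assume exponential progression at the planning rates and a constant, independent other-cause death hazard d, equal in both arms.

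- Progression hazard, control: −ln(1/12)/6 = 0.414 per month.
- Progression hazard, combination: −ln(7/12)/6 = 0.090 per month.
- With deaths counted, 6-month rate = exp(−6(λ + d)), median = ln 2/(λ + d), hazard ratio = (0.090 + d)/(0.414 + d). The table uses unrounded hazards.

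| d per month | Net probability of such a death by 6 months | Combination 6-month rate | Combination median (months) | Hazard ratio |
|---|---|---|---|---|
| 0 (same as deaths censored) | 0% | 58.3% | 7.7 | 0.217 |
| 0.02 | 1 − exp(−0.12) = 11.3% | 51.7% | 6.3 | 0.253 |
| 0.03 | 1 − exp(−0.18) = 16.5% | 48.7% | 5.8 | 0.270 |
| 0.05 | 1 − exp(−0.30) = 25.9% | 43.2% | 5.0 | 0.301 |

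A smaller input gives a smaller gap. At a 5% net probability by 6 months, the combination rate is 0.583 × 0.95 = 55.4% and the hazard ratio 0.233. In the control arm the rate moves little: 8.3% × exp(−0.12) = 7.4% and 8.3% × exp(−0.30) = 6.2%.

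**Hazard ratio when the arms differ.** The favourable shift depends on equal death hazards. If such deaths occurred only in the control arm at 0.05 per month, the hazard ratio with deaths counted would be 0.090/(0.414 + 0.05) = 0.19, below 0.217, and censoring would make the combination look worse. If they occurred only in the combination arm, it would be (0.090 + 0.05)/0.414 = 0.34.

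**The case against.** The strongest reply is that the SAP nowhere says how the main analysis treats these deaths. That they are censored or omitted is inferred from one sentence about a sensitivity analysis, and the two treatments give different curves. The intention-to-treat heading of Table 2 also sits badly with leaving patients out. This stands as a limit on certainty. It does not supply an analysis that counts the deaths: none is stated.

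A reader might infer more, and the documents do not support it:

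- That no death without documented progression is ever counted. The sentence covers only deaths from a cause other than progressive disease. A death attributed to the cancer but without a scan may be counted; the SAP is silent.
- That the reported figures are overstated in any event. With no such death there is no bias, and the effect on the hazard ratio depends on how the deaths fall between arms.
- That fatal toxicity would be hidden. Table 3 has a row for adverse events leading to death, serious events are tabulated by Protocol 8.3.5.1 and SAP 7.1, and overall survival is defined as time to death. The competing-risk sentence that SAP 7.1 adds for overall survival is a separate matter.
- That the primary test is affected. It is the binomial comparison at 180 days, with its own rule ("Patients unevaluable for progression at 6-months due to a non-progression related event will be excluded from analysis"). Sample size rests on that test alone.

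The shift is also modest against the trial's precision. With 12 events per arm, the standard error of the log hazard ratio is about √(1/12 + 1/12) = 0.41, so an estimate of 0.22 has a rough 95% interval of 0.10 to 0.48, which contains 0.25 to 0.30. That limits the practical weight but does not make the label correct: the shift is systematic, and the rates and medians carry it too.

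**Conclusion.** The point holds in limited form and should be fixed. As written, no stated analysis treats a death from a cause other than progressive disease as a progression-free survival event. With respect to those deaths, Figure 1 A/B and Table 2 would report time to progression under another name. If such a death occurs and is censored, the curve is biased upward from that point. If the death hazards are equal in the arms, the hazard ratio also looks too favourable.

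On an assumed 0.02 to 0.05 per month in both arms, the combination arm's 6-month rate is overstated by about 7 to 15 percentage points (58.3 − 51.7 = 6.6; 58.3 − 43.2 = 15.1) and its median by 1.4 to 2.7 months. The death rate, the exponential form, independence and equality between arms are all assumptions, and the handling in the main analysis is inferred. The weight is moderate because this is a supplementary analysis and not the primary test.

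**What to change.** In SAP 7.1, define the progression-free survival event for the log-rank, Cox and implied Kaplan-Meier analyses as the first of RECIST 1.1 progression or death from any cause, with patients without an event censored at their last evaluable scan. Apply this to Figure 1 A/B and Table 2.

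State three further rules, because otherwise late deaths after long unobserved periods would enter as events without comment:

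- deaths after a start of non-trial therapy, since disease-status follow-up ends there (Protocol 4.8 and Table 8, footnote a);
- deaths after missed scans or long gaps, since off-treatment status may come from 90-day telephone calls (Protocol 4.9);
- deaths attributed to progressive disease without a documenting scan.

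Keep the Fine-Gray analysis as a sensitivity analysis and label it time to progression. If the sponsor prefers to leave the event unchanged, relabel the outcome, Figure 1 A/B and the progression rows of Table 2 as time to progression.

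The cost is a short paragraph in the SAP and no new data collection. The downside is that the reported progression-free survival figures become somewhat less favourable if such deaths occur. The wording should be settled before the analysis is run.

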4.8 Patient Withdrawal/Discontinuation Criteria

Patients may withdraw consent at any time for any reason or be dropped from the trial at the discretion of the investigator should any untoward effect occur. In addition, a patient may be withdrawn by the investigator or the Sponsor if enrollment into the trial is inappropriate, the trial plan is violated, or for administrative and/or other safety reasons. Specific details regarding assessments to be done at an End of Treatment (EOT) visit at time of discontinuation or withdrawal are provided in Section 6.1.7.3.

A patient must be discontinued from the trial for any of the following reasons:

- The patient or legal representative (such as a parent or legal guardian) withdraws consent.
- Confirmed disease progression
- Unacceptable adverse experiences as described in Section 4.2.4
- Inter-current illness that prevents further administration of treatment
- Investigator's decision to withdraw the patient
- The patient has a confirmed positive serum pregnancy test
- Noncompliance with trial treatment or procedure requirements
- The patient is lost to follow-up
- Completed 24 months of uninterrupted treatment with pembrolizumab or 35 cycles of trial treatment whichever is later. 24 months of trial medication is calculated from the date of first dose.
- Administrative reasons

The End of Treatment and Follow-up visit procedures are listed in Section 5 (Trial Schedule) and Section 6.1.7 (Visit Requirements). After the end of treatment, each patient will be followed for 30 days for adverse event monitoring (serious adverse events will be collected for 90 days after the end of treatment as described in Section 6.2.3.1). Patients who discontinue for reasons other than progressive disease will have post-treatment follow-up every 90 days for disease status until disease progression, initiating a non-study cancer treatment, withdrawing consent or becoming lost to follow-up, or the end of the trial, whichever occurs first.

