6.1.2.6 Tumor Imaging and Assessment of Disease

The patient's pancreatic cancer will be evaluated by the investigator based on tumor assessments using RECIST 1.1 and iRECIST criteria (Appendix 5).

Tumor assessments for evaluation of response will be conducted using CT or MRI, approximately every 9 ± 1 weeks until trial discontinuation or disease progression, whichever is later. All sites of disease must be followed using the same baseline assessment method.

CT is the preferred imaging modality for this study. I.V. contrast should be administered, unless medically contraindicated.

If CT with I.V. contrast is contraindicated, the alternative is to acquire a CT of the chest without contrast and MRI of the abdomen and pelvis with gadolinium contrast.

Other protocols, such as non-contrast CT of chest abdomen pelvis, should not be performed. For CT scans oral contrast should be administered in addition to IV contrast. Radiolucent agents (e.g., water) are generally preferred over radiopaque agents (e.g., iodine and barium-based agents).

All target lesions will be measured by consistent imaging techniques for each patient throughout the trial. Suitable imaging techniques include CT-scan, or MRI. The same technique should be used for each evaluation in an individual patient. Copies of the scans must be available for review.

In addition, a central radiologist, blinded to the treatment assignment, will perform an independent read of each scan, assessing tumor response using RECIST 1.1 and iRECIST criteria (Appendix 5).

In the event that PD by RECIST 1.1 or iUPD is determined, a repeat scan must be performed within 4 - 6 weeks to confirm PD. Trial treatment may be continued during this time (past the initial PD assessment) but only if patient is clinically stable as defined by:

- No worsening of performance status

- No clinically relevant increase in disease related symptoms
- No requirement for intensified management of disease related symptoms (analgesics, radiation, palliative care)

If the investigator assesses a patient to have PD (defined by RECIST 1.1), the central radiologist will review the scan to confirm the PD, prior to the discontinuation of trial treatment.

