6.1.7.3 End of Treatment (EOT)

The patient will continue on maintenance therapy until there is evidence of clear-cut tumor progression, has treatment ending toxicities, or withdraws from treatment (refer to section 4.8). The following assessments will be performed within 5 days after completing the last dose of trial medication or before the initiation of a new anti-cancer treatment, whichever comes first:

- Directed physical exam
- ECOG Performance Status (see Appendix 4)
- Vital signs
- ECG
- Hematology: CBC with differential and platelet count
- Serum chemistries
- TSH, T3, T4
- CA19-9 (or CEA or CA-125 if not expressers of CA19-9)
- Urinalysis
- Serum β -HCG pregnancy test (for WOCBP)
- Central lab blood sample, 2 X10 mL vials
- Concomitant medication
- Patient to complete the PPCB App (Appendix 6)

- Provide Fecal Swab collection kit and review instructions (Appendix 9) with patient for return of sample within 72 hours of collection (coordinate with 30 day Safety Follow-Up visit)
- CT/MRI scan to evaluate disease status (using same imaging method as Baseline). Obtain De-identified dicomm encoded CT scan for central lab (Appendix 7).
- AEs using the NCI CTCAE Version 4.0 (see Appendix 3)
- Review contraception use as required by protocol Section 4.7.2 (where applicable)
- Confirm contact information for patient and a designated family member and remind patient of FU telephone contact that will be conducted every 90 days for survival status following the 30 - day follow-up visit.

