6.2 Assessing and Recording Adverse Events

An adverse event is defined as any untoward medical occurrence in a patient or clinical investigation patient administered a pharmaceutical product and which does not necessarily have to have a causal relationship with this treatment. An adverse event can therefore be any unfavorable and unintended sign (including an abnormal laboratory finding, for example), symptom, or disease temporally associated with the use of a medicinal product or protocol-specified procedure, whether or not considered related to the medicinal product or protocol-specified procedure. Any worsening (i.e., any clinically significant adverse change in frequency and/or intensity) of a preexisting condition that is temporally associated with the use of the pembrolizumab and /or paricalcitol, is also an adverse event.

Adverse events may occur during the course of the use of pembrolizumab and/or paricalcitol in clinical trials, or as prescribed in clinical practice, from overdose (whether accidental or intentional), from abuse and from withdrawal.

Progression of the cancer under study (pancreatic cancer) is not considered an adverse event.

All adverse events that occur after the consent form is signed but before treatment allocation/randomization must be reported by the investigator if they cause the patient to be excluded from the trial, or are the result of a protocol-specified intervention, including but not limited to washout or discontinuation of usual therapy, diet, placebo treatment or a procedure.

From the time of treatment allocation/randomization through 30 days following cessation of treatment, all adverse events must be reported by the investigator. Such events will be recorded at each examination on the Adverse Event case report forms/worksheets. The reporting timeframe for adverse events meeting any serious criteria is described in section 6.2.3.1. The investigator will make every attempt to follow all patients with non-serious adverse events for outcome.

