8.2 Sample Size Considerations

The primary endpoint is the percentage of patients progressing at 6 months. Based on a contemporary control of no maintenance after best response to prior chemotherapy⁸, the control arm with pembrolizumab alone is expected to have only 8% of patients with no progression at 6 months. To be of clinical interest, at least 58% of patients must be progression-free at 6 months on the pembrolizumab plus paricalcitol arm. A sample size of 12 patients per arm will provide 90% statistical power to detect this difference assuming a one-sided alpha level of 0.05. A one-sided test was selected as we are only interested in the combination if it decreases the percentage of patients progressing at 6 months. This sample size estimate was obtained using binomial enumeration of all possible outcomes to compare two independent binomial proportions (Pearson's chi-squared test) using PASS 15.¹⁸ A statistical concern is that the Pearson chi-squared test does not guarantee the alpha level. We confirmed that we have adequate statistical power using the Miettinen & Nurminen¹⁹ exact likelihood score method (89% power) using Pass 15.

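### Toxicity is compared as crude proportions over treatment times that differ by arm if the combination works, and the side of the toxicity test is not stated

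*SAP*

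**What the plan says.** SAP section 5 defines the toxicity window as "From initial treatment to end-of-treatment". SAP 7.1 includes every patient who received any trial treatment and says: "The proportion of patients in each arm with toxicity will be compared using a chi-squared test or Barnard's exact unconditional test". The sentence ends by referring back to the method outlined earlier in the section. There, the primary endpoint is compared "using a one-sided test of binomial proportions (equivalent to a Pearson's chi-squared test"), with Barnard's test as the fallback. SAP Table 3 (grade 3 or higher events) has a P value column.

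Protocol 6.1.7.3 sets the length of treatment: "The patient will continue on maintenance therapy until there is evidence of clear-cut tumor progression", or until treatment-ending toxicity or withdrawal. Protocol 4.8 adds an upper limit: "Completed 24 months of uninterrupted treatment with pembrolizumab or 35 cycles of trial treatment whichever is later".

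Neither document plans an exposure-adjusted rate, a time-to-first-event analysis or a common observation window. Protocol 8.3.3 lists and averages doses. Protocol 8.3.5.1 tabulates AEs.

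The windows also differ. Protocol 6.2 requires that "through 30 days following cessation of treatment, all adverse events must be reported by the investigator", which is longer than the SAP section 5 window, while SAP 7.1 gives a start but no end.

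**The concern.** Time at risk for an AE ends when treatment ends, and treatment usually ends at progression, which is the outcome the combination is meant to delay. Randomisation balances baseline factors, but it does not balance time at risk after that point. The proportion of patients who ever had an AE therefore mixes toxicity with duration.

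Evaluating toxicity between arms is the first secondary objective. If the trial succeeds as designed, the planned comparison could attribute to paricalcitol events that reflect only longer treatment.

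Sidedness is a separate matter. If the toxicity test inherited the one-sided efficacy direction, it could not flag excess harm on the combination.

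**Working it through.** **Planning rates.** Protocol 8.2 says "the control arm with pembrolizumab alone is expected to have only 8% of patients with no progression at 6 months", against at least 58% on the combination, with 12 patients per arm and one-sided alpha 0.05. Enumerating all 13 × 13 outcomes with the uncorrected Pearson test gives 90.3% power (stated: 90%). With the Miettinen-Nurminen factor it gives 89.0% (stated: 89%). The plan's figures reproduce.

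**Inputs.**
- 6 months = 180 days (SAP section 5); treatment cap taken as 730 days (Protocol 4.8).
- Scans "approximately every 9 ± 1 weeks until trial discontinuation or disease progression" (Protocol 6.1.2.6), taken as every 63 days.
- Dosing past first progression may continue to a repeat scan at 4–6 weeks if the patient is clinically stable (Protocol 6.1.2.6), taken as 35 days.
- Assumed: exponential progression times; the same constant hazard of a first AE in both arms, at 0.05, 0.10 or 0.20 per month of 30.4 days.

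**Time on treatment, stopping at the moment of progression.** λ = −ln(S)/180.
- Control: −ln(0.08)/180 = 0.01403 per day.
- Combination: −ln(0.58)/180 = 0.003026 per day.
- Mean = (1 − exp(−730λ))/λ = 71 versus 294 days, ratio 4.1.

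**Time on treatment, stopping at scans.** A patient who progresses between scans k−1 and k stops at day 63k, with probability S(63(k−1)) − S(63k).
- Means: 107 versus 323 days, ratio 3.0.
- With 35 more days: 142 versus 354 days, ratio 2.5.

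**Crude incidence.** With continuous stopping it is h/(h+λ) × (1 − exp(−730(h+λ))). At 0.10 per month, h = 0.10/30.4 = 0.003289 per day.
- Control: 0.003289/0.01732 × 1.000 = 19%.
- Combination: 0.003289/0.006316 × 0.990 = 52%.

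With scan-based stopping it is 1 − Σ P(stop at t) × exp(−ht).

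**False signals.** The last column is the chance that a two-sided 0.05 chi-squared test rejects with 12 per arm, by enumeration, when paricalcitol adds no toxicity.

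| Stopping model | AE hazard per month | Control | Combination | Rejects |
|---|---|---|---|---|
| Continuous | 0.05 | 10% | 34% | 26% |
| | 0.10 | 19% | 52% | 41% |
| | 0.20 | 32% | 68% | 49% |
| 9-weekly scans | 0.05 | 16% | 37% | 21% |
| | 0.10 | 28% | 56% | 32% |
| | 0.20 | 47% | 75% | 32% |
| Scans + 35 days | 0.05 | 20% | 41% | 19% |
| | 0.10 | 36% | 61% | 27% |
| | 0.20 | 58% | 80% | 22% |

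Working in calendar months with 1/12 and 7/12 (Protocol synopsis) moves the first row to 11% versus 35%, with the same 26% rejection. Adding a 30-day tail to continuous stopping at 0.10 gives 27% versus 56%.

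**Where it fades** (0.10 per month, continuous stopping).
- First 21 days: 5.8% versus 6.5%.
- Combination at only 22% progression-free (the sunitinib arm cited in Protocol 1.3 had 78% progressing): 19% versus 28%, and the test rejects in about 7%.
- No difference in progression: no gap.

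**Check of the remedy** (0.10 per month). First events per patient-month at risk are 0.100 in both arms. If patients stay on treatment to the first scan, 9-week incidence is 1 − exp(−0.10 × 63/30.4) = 18.7% in both. If progressors stop at once, it is 12.6% versus 17.1%, and the test rejects in about 4%.

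**Sidedness.** A one-sided 0.05 test for less toxicity on the combination rejects in at most 0.4% of trials across the nine rows, and by construction it cannot reject for excess harm.

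**The case against.** **Sidedness.** A reader might infer that the SAP plans a one-sided toxicity test that cannot detect harm. The documents do not say so. The toxicity sentence names no side. Its reference back may mean only the rule of chi-squared first and Barnard otherwise. The sole reason given for one-sidedness (Protocol 8.2) concerns progression. Nor would an inherited efficacy-direction test make the combination look more toxic; it would hide harm. What stands is an ambiguity, separate from the exposure problem.

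**Size.** A reader might also take the fourfold exposure ratio and the 26–49% false-signal rates as the size of the problem. Those figures assume that treatment stops the moment progression occurs. The trial's scan schedule and permitted dosing past first progression reduce them to a ratio of 2.5–3.0 and 19–32%. Barnard's test, the stated fallback, gives about 17–20% in the mildest of the three stopping models. This objection stands in part: the size falls, but the direction does not change.

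**Consequence.** Crude on-treatment incidence correctly describes what patients experienced. No decision rule uses the toxicity P value, dose listings would show unequal exposure, and an independent medical monitor receives an unblinded report (Protocol 9.8.2). All of this is fair. The difficulty lies in reading the between-arm gap as an effect of paricalcitol, which a P value beside crude proportions invites.

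**Conclusion.** The concern holds in a limited form. If the combination delays progression as planned, AEs that accrue steadily would appear more often on it even if paricalcitol added none. Under the assumed hazards, false signals occur in about 19–49% of trials against a nominal 5%, and the lower part of that range better reflects the trial's scan schedule.

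This rests on the planning rates, exponential progression and an equal, constant AE hazard that is assumed rather than documented. Early AEs are little affected. The primary analysis is untouched. The sidedness of the toxicity test is unstated and needs a clarifying line.

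**What to change.** In SAP 7.1 and Table 3:

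1. Keep the crude table as description.
2. Add, by arm, patients with a first event per patient-month at risk, with a rate ratio and confidence interval.
3. Add incidence within the first 9 weeks, up to the first scheduled scan.
4. Base the between-arm toxicity comparison on items 2 and 3.
5. State that toxicity tests are two-sided.
6. Reconcile the SAP's end-of-treatment window with the protocol's 30-day AE and 90-day serious AE reporting windows, and use the same window for events and time at risk.

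AE dates (Protocol 6.2.4) and dosing are already collected, so the cost is a little more analysis, with no new visits or patients. The downside is that the rates assume a roughly constant hazard, which is why the 9-week incidence is shown beside them. The 9-week figure is itself an equal-exposure comparison only as far as patients remain on treatment to the first scan.
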